8.4.3 Lost to Follow-up

Subjects who do not return for scheduled Follow-up Visits, as defined by the visit window, and cannot be contacted, are to be considered lost to follow-up. All attempts to contact the subject should be documented and kept with the subject's source documentation, and the applicable eCRFs will be completed. The date of exit reported shall be the date of last in-clinic study visit.

8.4.4 Treatment Withdrawal Follow-up Procedure

Exit Visit assessments should be completed for discontinued subjects.

9 Treatment Plan

The study will be conducted at approximately 13 investigative sites located in the US by Investigators who are determined by Bausch + Lomb to be suitably qualified by training and experience to conduct this study. Principal Investigators will be identified on the Device Investigator Agreement Form.

In the event that selected sites do not meet full enrollment, the Sponsor may decide to increase enrollment as needed at other currently active sites and/or additional site(s) may be added to satisfy the enrollment requirements of the study.

9.1 Randomization and Methods of Assigning Subjects to Treatment Groups

Subjects will be randomized to one of 2 treatment arms at a 1:1 ratio, wearing either Test or Control lenses in both eyes for the duration of the study. Randomization will be stratified by site, ancestry (Chinese, Non-Chinese), and sphere power sign (positive, negative).

Subjects will be randomized sequentially.

The randomization scheme will be produced prior to study enrollment by an unmasked statistician not otherwise involved in the trial. An unmasked designee at each site will be responsible for dispensing the study lenses according to the randomized treatment assignments. Lenses will be dispensed directly to the subject by the unmasked designee, thereby maintaining Investigator masking. In an effort to ensure that the Investigator remains masked, the unmasked designee MUST dispense the study lenses and MUST remove foils from their blister packs out of the Investigator's sight immediately prior to dispensing. Unworn (unopened) lenses that are returned by the subject to the site must be returned in a manner so as not to unmask the Investigator and other staff members at the site (ie, returned in an opaque bag or container labeled with subject identifiers). The unmasked designee will be responsible for physically examining the unopened lens blister package labeling to ensure the appropriate lenses were returned, and will document the return of these lenses in the CTM Product Accountability Log. The Investigator should contact the Medical Monitor prior to emergency unmasking of study arm assignment. In an urgent situation, however, where knowledge of the study arm assignment is critical to subject safety, the code may be broken by requesting the allocated treatment for that subject from the unmasked designee.

The Investigator must notify the Sponsor/Medical Monitor and/or Study Manager as soon as possible after emergency unmasking. In addition, the Investigator must record the date, time, and reason for unmasking the study arm assignment in the source documentation.

Study Monitors will become unmasked during site visits as they perform reconciliation activities and/or review randomization assignments, product accountability records, product inventory, and subject records. Study Monitors must take care not to unmask the Study Manager, other Bausch + Lomb staff, Contract Research Organization (CRO) staff, or site staff during the study.

9.2 Concomitant Medications

Subjects will be instructed to use their habitual rewetting drops as needed during the study. Other contact lenses/solutions are not allowed to be used by subjects during the study. All concomitant medications (ocular, systemic or topical) that have been taken in the past 30 days before signing the ICF and during the course of the study will be collected.

In the event that a subject requires medical treatment (prescription medication) for an ocular condition, treat the subject as appropriate to prevent further complications and to potentially resolve the event.

9.3 Treatment Administration and Compliance

The Investigator or other designee will review instructions and warnings for lens wear, lens care, handling, cleaning, and disinfecting with the subject. Any subject who does not follow instructions to a degree that, in the Sponsor or Investigator's opinion, jeopardizes the subject's well-being or the validity of the study, must be discontinued (see [Section 8.4](#)).

9.4 Protocol Deviations

The date of and reason for deviations will be documented in all cases. Significant or major protocol deviations impacting the safety of the subject or the integrity of the study must be reported by the Investigator to the IRB immediately. Reporting of all other protocol deviations must adhere to the requirements of the governing IRB.

Subjects may continue to participate until the end of the study, unless the protocol deviations put the subject at risk or the subject's condition requires that they be discontinued from the study.

10 Study Materials and Management

Bausch + Lomb will provide all study materials at no charge to the Investigator. Sites will be provided with dispensing sets for both the Test and Control lenses. All other materials will be provided to the site prior to the start of the study.

Subjects will be given an adequate supply of study lenses to wear on a daily disposable basis for the duration of the study.

Subjects will be provided with lens cases in which to dry stack their used lenses. All used lenses and blister foils will be returned at 1 week (Visit 3), 1 Month (Visit 4), 3 Months (Visit 5), and Exit Visits and all unused lenses will be returned to the Sponsor at end of the study.

Subjects will be instructed to use their habitual rewetting drops as needed during the study. Use of other contact lenses or care products is not allowed.

10.1 Investigational Product, Biotrue ONEday for Astigmatism

The Test Product in this case is the Biotrue ONEday for Astigmatism Soft Contact Lens. The description is as follows:

Diameter: 14.5 mm

Base Curve: 8.4 mm

Material: nesofilcon A

Spherical Power: Plano to -6.00D (in 0.25D steps);

Cylinder Powers; -.75, -1.25, -1.75

Axis: 10°, 20°, 60°, 70°, 80°, 90°, 100°, 110°, 120°, 160°, 170°, 180° (12 axes)

Cylinder Powers; -2.25

Axis 20°, 90°, 160°, 180° (4 axes)

Power: -6.50 to -9.00 (in 0.50D Steps);

Cylinder Powers; -.75, -1.25, -1.75

Axis: 10°, 20°, 70°, 80°, 90°, 100°, 110°, 160°, 170°, 180° (10 axes)

Spherical Power: +0.25D to +4.00D (in 0.25D steps);

Cylinder Powers: -0.75D, -1.25D, -1.75D

Axis: 20°, 70°, 90°, 110°, 160°, 180° (6 axes)

Orientation Mark at 6 o'clock.

10.2 Investigational Control Product, 1-Day Acuvue Moist for Astigmatism Contact Lens

The Control Product in this case is the 1-Day Acuvue Moist for Astigmatism contact lenses with the following description:

Diameter: 14.5 mm
Base Curve: 8.5 mm
Material: etafilcon A

Spherical Power: Plano to -6.00D (in 0.25D steps);
Cylinder Powers: -.75, -1.25, -1.75
Axis: 10°, 20°, 60°, 70°, 80°, 90°, 100°, 110°, 120°, 160°, 170°, 180° (12 axes)

Cylinder Powers: -2.25
Axis 20°, 90°, 160°, 180° (4 axes)

Spherical Power: -6.50 to -9.00 (in 0.50D Steps);
Cylinder Powers: -.75, -1.25, -1.75
Axis: 10°, 20°, 70°, 80°, 90°, 100°, 110°, 160°, 170°, 180° (10 axes)

Spherical Power: +0.25D to +4.00D (in 0.25D steps);
Cylinder Powers: -0.75D, -1.25D, -1.75D
Axis: 20°, 70°, 90°, 110°, 160°, 180° (6 axes)

Orientation Marks at 3 and 9 o'clock.

The Investigator should refer to [Appendix C](#) for the fitting guide for the study lenses.

10.2.1 Packaging and Labeling

The Test lenses (Biotrue ONEday for Astigmatism) used in this study will be provided in the currently marketed packaging. The blister label will contain the following information:

- lens power
- base curve
- lens diameter
- lot number
- expiration date
- manufacturers name

The Control lenses (1-Day Acuvue Moist for Astigmatism) used in this study will be provided in the currently marketed packaging. The blister labels will contain the following information:

- lens power

- base curve
- lens diameter
- lot number
- expiration date
- manufacturer's name

The commercial cartons for both Test and Control lenses will contain an additional label: "Study 885 For Clinical Trial Use Only".

10.2.2 Storage, Handling, and Disposal of Study Lenses

All Test and Control lenses provided by the Sponsor must be stored in a secure location accessible only to study personnel and maintained at room temperature. No lenses should be disposed of. All lenses, worn or unworn, will be returned to the Sponsor.

10.2.3 Study Lens Preparation

The Investigator should refer to the Fitting Guide (see [Appendix C](#)) for fitting the Test and Control lenses.

10.2.4 Administration

Test or Control lenses will be worn on a daily disposable wear basis. One hundred twenty (120) new study lenses will be shipped to the site per eye. Up to 110 new study lenses will be dispensed per eye at the Dispensing Visit to provide sufficient quantities to maintain a daily disposable wear modality for at least 102 days. Ten (10) study lenses will remain at the site for all Follow-up Visits.

After contact lens assessments are complete at Follow-up Visits, the Investigator will collect and store worn lenses for subsequent return to the Sponsor.

10.2.4.1 Subject Instructions

All subjects must be given Subject Instructions for the use of study lenses (refer to [Appendix B](#) for Subject Instructions). Subjects must comply with the instructions provided to them. Subject Instructions will be supplied to the Investigator by Bausch + Lomb for distribution to the subjects.

All subjects must refer to lens subject instructions for precautions and warnings related to contact lens wear. Subjects should refer to the package insert for precautions and warnings related to the use of this lens care product.

The Investigator or other designee must review, with the subject, the Subject Instructions and the precautions and warnings, as appropriate for the study.

Any subject who does not follow instructions to a degree that, in the Sponsor or Investigator's opinion, jeopardizes the subject's well-being or the validity of the study, should be discontinued.

10.2.4.2 Subject Diary

Subjects will be required to complete a paper diary. Subjects will be provided with a reminder to complete the diary to capture wear experience on a weekly basis until they exit the study. Each enrolled subject will be provided with instructions for completing the diary after 7 days of lens wear. There will be a specified timeframe in which the diary must be completed.

10.3 Study Lens Accountability

The unmasked designee at each site will be responsible for keeping current and accurate records of the amount of study lenses received and dispensed, and their disposition. The study lenses must be stored under the appropriate conditions in a secure area and are to be dispensed only to subjects enrolled in the study, in accordance with the conditions specified in this protocol. During the course of the study, the unmasked designee must maintain an inventory of all study lenses dispensed to or returned by the subject, including subject identifiers. A Clinical Trial Materials (CTM) Product Accountability Log will be provided to the sites to maintain records of the study lenses assigned to each enrolled subject.

At time points throughout the study and/or upon completion of the study, the Sponsor/Sponsor's representative may review the Product Accountability Log to verify the Investigator's accountability records.

The subject will be dispensed up to 110 lenses for the entire study at the Dispense Visit. The subject will drystack up to 10 worn lenses per left eye and 10 worn lenses per right eye in one lens case. The subject will return all blister foils for the worn lenses and the drystack lens cases at each visit. The unmasked designee will collect the lens cases and blister foils, and complete the Product Accountability Log. The drystacked lens cases will be placed in a resealable plastic bag with a 'Worn Lens Label' label adhered to the bag. The resealable bags from each visit will be collected in one white opaque bag per subject. The opaque bag will be labeled with subject ID, Investigator ID, and Investigator name. Do not permanently seal the opaque bag until subject accountability at end of the study. At the end of the study, all unworn/unopened lenses returned by the subject should be in the subject's white opaque bag. Only the unmasked designee will handle the worn and unworn/unopened lens returns and white opaque bags. The unmasked designee must enter all lenses dispensed and returned immediately into the CTM Product Accountability Log. Once the Product Accountability Log has been verified by the study clinical research associate (CRA) (with signature), close and seal each subject's white opaque bag. Following verification, and as directed by the

Sponsor, all subject's sealed opaque bags that include their worn and unworn study lenses must be returned at the end of the study to the Sponsor's CTM Supply Chain at the address listed below. FedEx tags will be provided to the sites for return of subject opaque bags.

[REDACTED]

[REDACTED]

[REDACTED]

[REDACTED]

10.4 Noninvestigational Products

Subjects will be instructed to use their habitual rewetting drops as needed during the study. The use of other contact lens care products is not allowed.

10.5 Responsibility

Subject data required by this protocol are to be transferred from the source to the eCRFs. The Investigator and his/her study site personnel will be responsible for completing the eCRFs. The Investigator is required to verify that all of the requested information is accurately recorded on the eCRFs by providing an electronic signature. All information requested on the eCRFs needs to be supplied, including subject identification and initials, date(s), assessment values, etc, and any omission or discrepancy will require explanation. All information on eCRFs must be traceable to source documents.

The study monitor will be responsible for reviewing and verifying the data recorded on the eCRFs per the study Monitoring Plan, utilizing the original source documentation and will query discrepant findings. The Investigator and study site personnel will be responsible for answering all queries.

The eCRFs will be submitted to Bausch + Lomb Global Clinical Operations for quality assurance review, data entry, and statistical analysis.

A copy of the eCRFs will be provided to the Investigator at the conclusion of the study, who must ensure that it is stored in a secure place.

11 Study Procedures and Evaluations

NOTE: All VA measurements MUST be made using a phoropter.

NOTE: Use the same keratometer at the Screening and Exit Visits.

11.1 Visit Schedule

11.1.1 Screening Visit

A Screening Log will be provided by the Sponsor to track all consented subjects that the Investigator interviews regarding the study. Once all available lines on the Screening Log have been completed, or the Investigator has fulfilled his/her quota of subjects, the Investigator will sign and date the form to verify that all the subjects who interviewed for the study have provided informed consent and Health Insurance Portability Accountability Act (HIPAA) authorization. The Investigator will send the bottom copy of each Screening Log to the Sponsor as soon as the quota of subjects for his/her site has been enrolled into the study. The Investigator will retain the original document for their records.

After obtaining written informed consent, prospective subjects will be screened to determine whether they meet the entry criteria for the study.

Screening will proceed as follows:

- a. Enter the subject information on the next available line of the Screening Log.
- b. Collect the following lens history information from the subject: average daily wearing time hours lenses worn on the day of this visit current lens brand and lens wear modality, current lens care products. Collect the relevant medical history for the past 2 years.
- c. Collect demographic and baseline information and perform the following baseline/Screening assessments (without lenses) and record in the subject's source document: uncorrected distance VA, autorefraction, spherocylindrical refraction, distance best spectacle-corrected visual acuity (BSCVA), keratometry, intraocular pressure (IOP) using the TonoPen or the Goldmann Applanation Tonometer, dilated fundus exam, direct ophthalmoscope exam (non-dilated).
- d. Perform a slit lamp examination (remove the lenses if the subject wore lenses to the visit). Record and diagram the results and findings in the subject's source document and appropriate eCRF:
 - any ungraded finding marked as "PRESENT"
 - any new corneal scars
 - any neovascularization within the central 6 mm of the cornea
 - any corneal staining
 - any corneal infiltrate (record details on the Corneal Infiltrates Evaluation Form [\[Appendix E\]](#))
 - any other graded slit lamp findings Grade 2 or greater
- e. If the subject is eligible, collect AE and Symptoms/Complaints information from the subject regarding their habitual lenses.

- f. Assign subject numbers to each eligible subject in ascending order. A log will be provided to each site to maintain a record of the subject numbers assigned to each enrolled subject. Record the assigned subject ID on the Screening Log.
- g. The unmasked designee will determine the eligible subject's randomized lens type (treatment group).
- h. The Screening Visit eCRF should be completed only if the subject is a "Screen Pass."
 - i. Conduct a diagnostic fitting evaluation for the Test or Control lenses to the lens the subject is randomized to, using the Fitting Sets provided. The prescription determined from this fitting assessment will be used to dispense/order Test or Control lenses according to the lens the subject is randomized to. The Investigator should ensure that the lens was inserted with the toric etch marks roughly at the 6 o'clock positions and /or allow the trial lenses to properly settle on the eye for a minimum of 5 minutes. Collect the following information for both study lenses using the study site's standard diagnostic fitting techniques:
 - Collect Symptoms/Complaints information using the Symptoms/Complaints Rating Scales in [Appendix A](#)
 - lens wettability
 - lens centration
 - lens movement
 - lens rotation
 - lens deposits

Record the lens parameters to be dispensed/ordered based on the diagnostic fitting.

- j. "Screen Fail" subjects are ineligible and non-dispensed and cannot be enrolled in the study if parameters are unavailable or fit is deemed unacceptable. The reason for screen failure must be documented and maintained with a copy of their ICF.
- k. Indicate on the Screening Log whether the subject is a "Screen Pass" or "Screen Fail." "Screen Fail" subjects are ineligible and cannot be randomized in the study. The reason for screen failure must be documented on the Screening Log and in the subject record, and maintained with a copy of their ICF.

Only "Screen Pass" subjects should be randomized in the study.

- l. Re-emphasize the exclusion criterion stating that if the subject is a female of child bearing potential and is pregnant and or breast feeding, she is ineligible to be a part of the study.

For each subject, use the Material Order Form for Study 885 to order the appropriate study contact lenses (test or control). Schedule the subject for their Dispensing Visit within 3 weeks as instructed by the Sponsor.

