who signs an ICF. All screened subjects must be entered onto the Screening Log, in the order in which they were consented, where they will be assigned a sequential subject identification (ID) number. Once a potential subject is consented and their initials are entered onto the Screening Log, the Investigator should proceed with Screening procedures.

Potential subjects are deemed either “Screen Pass” or “Screen Fail.” “Screen Fail” subjects have not met the study inclusion criteria or have met the exclusion criteria. “Screen Fail” subjects cannot be randomized. Subjects are considered enrolled when they have signed the ICF. The copy of their signed ICF and any information collected as part of screening (eg, source documents, etc.) must be kept in their medical records.

“Screen Pass” subjects have met all of the study inclusion criteria and have not met any of the exclusion criteria. Only “Screen Pass” subjects can be randomized to receive the study lenses.

Once a subject has signed the ICF, a subject is considered enrolled and must be accounted for at every visit until exited (completed, discontinued, or non-dispensed) from the study, even if they are not dispensed study materials.

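### Section 11.1.1 determines the assigned lens before the fit that decides Screen Fail, so exclusion from the Per Protocol primary analysis can depend on the arm

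*Combined protocol and SAP*

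**What the plan says.** Section 11.1.1 presents screening as a lettered sequence.

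- **Step e** already speaks of eligibility: "If the subject is eligible, collect AE and Symptoms/Complaints information from the subject regarding their habitual lenses".
- **Step g** looks up the assignment: "The unmasked designee will determine the eligible" subject's lens type.
- **Step h** restricts the record: "The Screening Visit eCRF should be completed only if the subject is a" Screen Pass.
- **Step i** orders the fitting: "Conduct a diagnostic fitting evaluation for the Test or Control lenses to the lens the subject is randomized to, using the Fitting Sets provided". It continues: "Collect the following information for both study lenses".
- **Step j** says of Screen Fails: "subjects are ineligible and non-dispensed and cannot be enrolled in the study if parameters are unavailable or fit is deemed unacceptable".
- **Step k** says of Screen Fails: "subjects are ineligible and cannot be randomized in the study".

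Section 8.2 agrees with step k: only Screen Pass "subjects can be randomized to receive the study lenses". Inclusion criterion 8 in the same section requires that the subject can be fitted in both the Test and the Control lens within the listed parameters.

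On the analysis side:

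- Section 12.6 lists ineligibility and non-dispensing as major deviations.
- Section 12.2.2 removes major deviators from PP.
- Section 12.3.2 makes PP the primary set, with no imputation.
- Section 12.2.1 defines ITT as randomized subjects judged eligible on assessments made before randomization.

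**The concern.** A subject who fails the step i fit has already had an assignment determined and a lens of that type on the eye. Step j then labels the subject a Screen Fail, a status that step k and Section 8.2 reserve for people who were never randomized. Both sets of instructions cannot be followed.

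The statistical issue is an exclusion after randomization that can depend on the arm, because only the assigned lens is fitted. If fit failure differs between lenses and is related to lens acuity, the PP comparison is biased. More failures with the Test lens favour a non-inferiority conclusion; more failures with the Control lens cost power.

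The fit judgment may also not be free of knowledge of the lens. Subjects are unmasked (Section 7.1), and Sections 10.1 and 10.2 give the two lenses different orientation marks, while rotation is assessed at this fitting.

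The ITT imputation, worst-case and tipping-point analyses in Section 12.3.2 could show the effect, but only if these subjects are recorded and kept. Two wordings work against that: step h withholds the Screening Visit eCRF from anyone who is not a Screen Pass, and step j calls these subjects ineligible.

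**Working it through.** **The plan's own figure (Section 12.1).** Success rate 0.925 in both arms, margin 0.10, one-sided alpha 0.025, power 80%:

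n = (1.960 + 0.842)² × 2 × 0.925 × 0.075 / 0.10² ≈ 109 per group.

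109 / 0.9 = 121.1, rounded up to 122 per group, 244 in total. The stated figures reproduce, and nothing below changes them.

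**Route out of the primary analysis.** Assignment (step g) → fit of the assigned lens (step i) → unacceptable fit, non-dispensed (step j) → major deviation (Section 12.6) → out of PP (Section 12.2.2) → not imputed (Section 12.3.2). The word eligible in steps e to g allows parameter availability to be settled before step g. It does not cover on-eye fit: step i is the only diagnostic fitting described, and it follows assignment.

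**Illustration of size.** Neither input below comes from the documents.

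- f = share of subjects who cannot be fitted in one of the lenses: 2% or 5%.
- s = success rate of those subjects in the other lens: 0.5, 0.8 or 0.925.

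The reference is the population that can be fitted in both lenses. Each arm starts at 109. The affected arm loses its unfittable subjects: 109 × 0.98 ≈ 107 or 109 × 0.95 ≈ 104. The other arm keeps its counterparts, so its success rate becomes

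p = (1 − f) × 0.925 + f × s.

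For s = 0.5, p = 0.98 × 0.925 + 0.02 × 0.5 = 0.9165, or 0.95 × 0.925 + 0.05 × 0.5 = 0.9038.

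The planned rule concludes non-inferiority when d − 1.96 × SE > −0.10, with unpooled sample variance. Its rejection probability was found by summing exact binomial probabilities over all outcomes.

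With no exclusion it is 3.0% at the null boundary (0.825 Test v 0.925 Control) and 80.3% at equality (0.925 in both). The 3.0% is a property of the Wald rule, not of the exclusion.

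| s | Test-unfittable, null boundary: false non-inferiority at f = 2% / 5% | Control-unfittable, true equality: power at f = 2% / 5% | Size of bias, points |
|---|---|---|---|
| 0.5 | 4.4% / 7.2% | 70.3% / 53.9% | 0.85 / 2.1 |
| 0.8 | 3.4% / 3.9% | 77.0% / 71.8% | 0.25 / 0.6 |
| 0.925 | 3.0% / 2.9% | 79.6% / 78.6% | 0 / 0 |

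Bias is f × (0.925 − s), for example 0.05 × 0.425 = 2.1 points. It is positive (towards Test) in the second column and negative in the third.

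**A harsher reference.** Suppose instead that every randomized subject counts and a fit failure is a non-success. With 122 per arm and an all-randomized Test rate of 0.825, dropping Test failures raises the PP Test rate to 0.825 / (1 − f), which is 0.842 at 2% and 0.868 at 5%. By normal approximation, the chance of concluding non-inferiority goes from 2.5% to 6.1% and 19.5%. This answers a different question, and shows how far the figure depends on how a fit failure is valued.

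**The case against.** The strongest reply is that the governing rule is clear and repeated. Section 8.2 and step k both bar Screen Fails from randomization, criterion 8 requires fit in both lenses, and steps e to g apply only to eligible subjects. A site that obeys these settles fit before step g, and the bias never arises. That would avoid the problem, but no both-lens fit is scheduled before step g, and step i orders a fit of the assigned lens only. Criterion 8 can also be read as parameter availability alone, and the phrase about both study lenses in step i may mean right and left.

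Second, other text gives a recording route. Section 8.3 discontinues subjects later found ineligible, Section 8.4.1 lists ineligibility at screening as a discontinuation reason to be documented, Section 11.1.4 has a non-dispensed exit status, and Sections 8.2 and 12.4 account for subjects. Read literally, Section 12.2.1 keeps a subject who was judged eligible before randomization. This stands and makes loss from ITT less likely. It does not affect the PP exclusion, and the wording of steps h and j still needs correcting.

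Third, a difference between arms may be small. Sections 10.1 and 10.2 list identical powers, cylinders, axes and diameter, with base curves of 8.4 and 8.5 mm, and subjects are habitual toric wearers. This is a fair limit on likely size. It does not show that on-eye fit fails equally often.

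Fourth, starting at 109 leaves out the dropout allowance. From 122 per arm, with fit failure the only loss and Control failing, power at f = 2% and 5% is 83.7% and 84.4% (s = 0.925), 81.3% and 78.3% (s = 0.8), or 75.0% and 60.6% (s = 0.5). The allowance absorbs much of the power loss if it is not needed for ordinary dropout. It does not address false non-inferiority.

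**Conclusion.** The concern holds; the section is wrong as written and should be fixed. Followed in letter order, Section 11.1.1 contradicts its own step k and Section 8.2, and opens a post-randomization exclusion from the primary analysis that can depend on the assigned lens.

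The size is unknown because the documents give no fit-failure rate. Bias requires failure that differs by arm and is related to acuity. Under the assumed one-arm failure rates of 2% to 5%, measured against the fit-in-both population, false non-inferiority lies between 2.9% and 7.2%, against 3.0% without exclusion. Power lies between 53.9% and 79.6%, against 80.3%, starting from 109 per arm. If failure is unrelated to acuity there is no bias, only lost subjects. Confidence is medium: the contradiction is plain in the text, but its effect depends on what sites do. The wording of step i on both lenses and the reading of criterion 8 are ambiguities, not contradictions.

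**What to change.** 1. Reorder steps g to k so that fit acceptability and parameter availability, as criterion 8 requires, are assessed and Screen Pass or Screen Fail is recorded before the assignment is determined or revealed.
2. Reconcile step i with criterion 8: state which lenses are fitted, and whether criterion 8 means on-eye fit or parameter availability.
3. Amend step h so that the Screening Visit eCRF is completed for every subject whose assignment was determined.
4. State in Section 12.2.1 that any randomized but non-dispensed subject stays in ITT and in the planned missing-data analyses.
5. Clarify Section 12.2.3, which equates dispensed with fitted, so that it is clear whether a subject who was trial-fitted but never dispensed enters the Safety Population, and under which lens.

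The cost is wording and the order of one visit, plus a short trial fit in the second lens if criterion 8 means on-eye fit. Section 10 supplies dispensing sets for both lenses but does not say whether these are the fitting sets of step i, so supply for a second trial fit needs confirming. The sample size stays at 109 evaluable and 122 enrolled per arm, 244 in total.
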